6.3 REPORTING/RECORDING OF AEs

Throughout the course of the study, all efforts will be made by the investigator to remain alert to possible AEs. The first priority will be the safety of the subject and providing appropriate medical intervention. The period of observation for collection of AEs starts at index procedure until study completion.

6.4 ADVERSE EVENTS REPORTING

The Investigator must complete and submit the AE Case Report Form (CRF) containing all information required by local and/or regional regulations to the Sponsor and Clinical Research Organization (CRO) by fax or email immediately (within 24 hours of awareness).

Sponsor Contact: [name]
[contact]
Email: [contact]

The AE CRF must be signed by a medically qualified investigator (as identified on the delegation of authority log). The signature confirms the accuracy and completeness of the SAE/SADE data as well as the investigator causality assessment including the explanation for the causality assessment.

In addition, the Investigator will report adverse events to the reviewing EC (as applicable) according to the local reporting requirements. Upon notification of SAEs, the Sponsor will initiate and complete a review and evaluation of the event within timeframes that will maintain reporting

compliance with applicable regulatory agencies. The Sponsor or designee will report all SAEs and device deficiencies that could have led to an SADE to the Competent Authority in accordance with EU Regulation 2017/745 and all applicable national regulations.

Investigators must submit safety reports as required by their EC within the required timelines. Documentation of the submission and receipt by the EC of should be retained by the study site.

In the event of a subject's death, the Investigator will make reasonable effort to obtain a copy of the autopsy report and/or death summary. The Investigator will determine the cause of death and its relationship to the investigational device; the Investigator will record results on the AE CRF. The Investigator will include copies of an autopsy report, if available, and/or a death summary with this form.

6.5 ANTICIPATED ADVERSE EVENTS

There are no anticipated Adverse Events specifically associated with the use of the CathVision ECGenius® system.

Arrhythmias requiring an EP procedure that are chronic but stable, and present at screening, should not be recorded as an AE. Changes in a chronic condition or disease that are consistent with natural disease progression are NOT considered AEs and should not be recorded. These medical conditions should be adequately documented in the subject's cardiac history. However, medical conditions present at enrollment that worsen in intensity or frequency in a manner inconsistent with the natural course of the disease during the EP and/or ablation procedures and during the study should be reported and recorded as AEs.

A recurrence of an atrial tachyarrhythmia requiring hospitalization in order to administer cardioversion within the blanking period is within the scope of treatment for chronic but stable AF patients. This will not be considered an adverse event. Self-limiting pericarditis attributable to the ablation procedure, defined as pleuritic chest discomfort with or without pericardial rub and ECG changes, is not considered an adverse event.

The expected rates of occurrence of these anticipated AEs using the study device are expected to be the same as the rate experienced when using commercially available EP recording systems for the same indication. The mitigations and treatments for these AEs will follow published guidance for the same AEs occurring with other commercially available devices¹.

Anticipated AEs associated with arrhythmia and EP procedures include, but are not limited to:

- Air embolism
- Allergic reaction (including anaphylaxis)
- Anesthesia reaction
- Angina
- Aorto-right atrial fistula
- Arrhythmias, including exacerbation of pre-existing atrial fibrillation
- Arterial-venous fistula
- Cardiac perforation/ tamponade

- Cardiac thromboembolism
- Cardiac or respiratory arrest
- Catheter entrapment
- Cerebrovascular incident / Stroke
- Chest pain/discomfort
- Congestive heart failure
- Coronary artery dissection
- Coronary artery spasm
- Coronary artery thrombosis / occlusion
- Death
- Diaphragmatic paralysis
- Endocarditis
- Esophageal ulceration
- Gastroparesis
- Heart failure / pump failure
- Hemoptysis
- Hemothorax
- Hypotension
- Hospitalization (initial and prolonged)
- Increased creatinine phosphokinase (CPK) level
- Infections
- Laceration
- Leakage of air or blood into the lungs or other organs due to perforation
- Left atrial esophageal fistula
- Major bleeding, requiring surgery or transfusion
- Myocardial infarction
- Obstruction or perforation or damage to the vascular system
- Pericarditis
- Pericardial effusion
- Phrenic nerve damage including Diaphragmatic paralysis
- Pleural effusion
- Pneumonia
- Pneumothorax
- Pulmonary edema
- Pulmonary embolism
- Pulmonary vein dissection
- Pulmonary vein thrombus
- Pulmonary hypertension
- Respiratory depression
- Skin burns
- Severe PV stenosis or complete occlusion, even asymptomatic
- Tamponade, potentially requiring surgery
- Temperature elevation or fever
- Transient Ischemic Attack (TIA)

- Thromboembolism
- Thrombosis
- Unintended complete or incomplete AV, Sinus node, or other heart block or damage
- Valve damage
- Vascular bleeding / local hematomas / ecchymosis
- Vasovagal reactions
- Ventricular tachyarrhythmia
- Volume overload

6.6 DEVICE DEFICIENCIES

Device deficiency is defined as an inadequacy of a medical device with respect to its identity, quality, durability, reliability, safety, or performance.

Note, device deficiencies include malfunctions and use errors. All device deficiencies that occur during the study will be recorded in the corresponding CRF.

Device malfunction: failure of an investigational medical device to perform per its intended purpose when used in accordance with the instructions for use.

User error: act or omission of an act that results in a different medical device response than intended by the manufacturer or expected by the user.

The Device Deficiency CRF is specific for reporting all device deficiencies that occur during the study, whether or not they were associated with an adverse event. Device Deficiency CRFs should be submitted to the Sponsor within 24 hours of the occurrence defining the device deficiency.

Anticipated device deficiencies and malfunctions from any standard of care EP system include, but are not limited to:

- Catheter deflection deficiency or failure
- Malfunction of a catheter electrode
- Malfunction of a catheter temperature sensor
- Unexpected termination of ablation due to internal system error
- Failure to initiate ablation due to internal system error
- Temporary or sustained loss of catheter navigation/visualization capability/signal

Record any CathVision ECGenius® system deficiencies and malfunctions, including but not limited to:

- ECGenius® system issues (Cube® EPAMP/RecSW)
 - Not able to power on
 - Power indicators not on
 - Not able to connect to the standard of care EP system
 - Not able to retrieve signal from standard of care EP system
 - Not able to power down
 - Database issues

- Backup data issues
- Not possible to clear fault without reboot
- ECGenius® Recorder Software
 - Malfunction
 - Loss of power
 - Loss of waveform
 - Recording issues (interruption, stop)
 - Not able to create patient
 - Not able to save patient
 - Live Mode issues (not able to create/resume patient, etc)
 - Review Mode issues (not able to retrieve a patient)
 - SW crashes
 - SW loses connection to EPAMP
 - Limitation: Only possible to review the latest recording file, while streaming is active
 - Bug: Not possible to use the notch filter, if high-pass and low-pass is set to 'None'
- Host Computer Malfunctions
 - Not able to boot/start
- User errors
 - Not recording data

7. STATISTICAL METHODS

7.1 SAMPLE SIZE CALCULATION

This prospective, single center, feasibility study is intended to collect data from patients in AF rhythm in order to test the feasibility of displaying changes in signal complexity. As a result, no formal statistical hypothesis was applied to derive the sample size. The selection of the sample size was made using a non-probability, purposive method.

If subjects receive treatment without meeting all the CIP-required conditions, they are counted in the Intent-to-Treat (ITT) population, they will not be deregistered from the clinical investigation, and they should complete all follow-up requirements. These subjects are considered CIP deviations, and are excluded from the sample size calculation and endpoint analysis. For a detailed description of the statistical analysis with respect to the enrolled population and deviations, refer to the Statistical Analysis Plan (SAP).

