4.5.2 SAFETY ENDPOINT

The safety endpoint of this study consists of the evaluation of adverse events and/or device deficiencies reported with the use of the CathVision ECGenius® System during the procedure until discharge.

The detailed methods to analyze the primary and safety endpoints will be included in the Statistical Analysis Plan (SAP).

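### Section 7.1 drops subjects treated outside the CIP conditions from endpoint analysis without exempting the safety endpoint

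*Combined protocol and SAP*

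**What the plan says.** Section 7.1 sets the rule for one group: "If subjects receive treatment without meeting all the CIP-required conditions". The conditions are not listed. Three things follow for these subjects:

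- On population, "they are counted in the Intent-to-Treat (ITT) population".
- On follow-up, "they will not be deregistered from the clinical investigation, and they should complete all follow-up requirements".
- On analysis, "These subjects are considered CIP deviations, and are excluded from the sample size calculation and endpoint analysis".

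The next sentence in 7.1 refers to the SAP for the handling of the enrolled population and of deviations.

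Section 4.5 names two endpoints. Section 4.5.1 makes technical success primary. On the other, Section 4.5.2 states: "The safety endpoint of this study consists of the evaluation of adverse events and/or device deficiencies". It also leaves the detailed methods for both endpoints to the SAP. Section 7.2 describes summary statistics and names no analysis set.

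**The concern.** The exclusion is worded for endpoint analysis in general, and safety is a named endpoint. A subject treated outside the CIP conditions has still had the procedure, normally with the investigational system connected. A safety summary is meant to describe everyone exposed. If 7.1 is followed as written, such a subject stays in the study, completes follow-up and has adverse events and device deficiencies on the CRF, yet does not appear in the safety endpoint summary. The ITT population that 7.1 assigns these subjects to is given no analysis, so it does not bring them back. With 15 to 30 subjects, each exclusion removes 1/30 = 3.3% to 1/15 = 6.7% of the sample.

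**Working it through.** **Step 1: does any other text restore these subjects to the safety summary?**

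- Section 7.1 excludes them from endpoint analysis with no limit by endpoint. Section 4.5 has two endpoints, so the literal scope is both.
- The ITT population appears only in 7.1 and no analysis is attached to it. No safety population is defined anywhere.
- Sections 6.2 and 6.6 require all adverse events and all device deficiencies to be recorded on CRFs. Section 6.4 governs reporting, and Section 3 promises detailed evaluation of each event. None of these says whose data enter the endpoint summary.
- Section 4.4.3 ties enrolment to confirmed eligibility. A summary of enrolled subjects would therefore not clearly recover someone treated despite an unmet criterion.

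The protocol text does not restore them.

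**Step 2: how much could it matter?** There is no plan figure to reproduce: the sample size is purposive, without a hypothesis (7.1). What follows is an illustration.

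Inputs: N = 15 or 30 (Section 4.4). Assumed, because the documents give no rates: exactly one subject with an event; k = 1 or 2 subjects excluded; exclusion unrelated to the event. Intervals are exact (Clopper-Pearson) 95%.

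Formulas:

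- Chance that the event subject is excluded = k/N; the summary then shows 0/(N−k).
- Chance that the event subject is retained = (N−k)/N; the summary then shows 1/(N−k).
- Expected rate = [(N−k)/N] × [1/(N−k)] = 1/N, the same as with everyone kept.

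| N | k | All treated | Event subject excluded | Chance | Event subject retained | Chance | Expected rate |
|---|---|---|---|---|---|---|---|
| 15 | 1 | 1/15 = 6.7% (0.2–31.9) | 0/14 = 0% (0–23.2) | 6.7% | 1/14 = 7.1% | 93.3% | (14/15)(1/14) = 6.7% |
| 15 | 2 | 1/15 = 6.7% (0.2–31.9) | 0/13 = 0% (0–24.7) | 13.3% | 1/13 = 7.7% | 86.7% | (13/15)(1/13) = 6.7% |
| 30 | 1 | 1/30 = 3.3% (0.1–17.2) | 0/29 = 0% (0–11.9) | 3.3% | 1/29 = 3.4% | 96.7% | (29/30)(1/29) = 3.3% |
| 30 | 2 | 1/30 = 3.3% (0.1–17.2) | 0/28 = 0% (0–12.3) | 6.7% | 1/28 = 3.6% | 93.3% | (28/30)(1/28) = 3.3% |

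An observed event can become a reported zero, but under neutral exclusion this is the less likely branch. If more than one subject had an event, losing one of them would not give zero.

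**The case against.** The strongest reply is that the SAP may already settle this. Section 7.1 points to it for exactly this topic, 4.5.2 points to it for the safety methods, and an all-treated safety set may be defined there. That stands as a limit on what can be concluded. It does not remove the sentence in 7.1: if the SAP does define such a set, the two texts conflict and 7.1 still needs correcting.

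A second reply is that Sections 3, 6.2, 6.4 and 6.6 plainly intend every event to be recorded, reported and evaluated, so the sentence is loose drafting in a sample-size section. As a reading of intent this is fair. A reader might infer from 7.1 that events in these subjects would be lost or go unreported; the documents say the opposite. What remains open is their place in the endpoint summary.

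A third reply is that little is at stake. The system records passively alongside a standard one and guides no care (3, 4.2), has no anticipated adverse events of its own (6.5), and the study has no hypothesis and no statistical stopping criterion (7.1, 7.2). The eligibility criteria are few, so few subjects may be affected. This stands and sets the severity.

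**Conclusion.** The point holds as a matter of protocol wording, at low severity. Section 7.1, followed literally, takes exposed subjects out of the safety endpoint summary, and nothing else in the protocol puts them back.

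Three stronger readings are tempting and not supported:

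- *That the final report will omit these subjects.* The SAP text needed to decide this is not in the document reviewed.
- *That the rule makes the device look safer, or removes technical failures.* Nothing links the unmet conditions to events or to signal quality. If they are unrelated, the expected safety rate is unchanged (6.7% at N=15, 3.3% at N=30), and so is expected technical success. A fall to 0% has probability 3.3% to 13.3%, and only under the assumed single event subject and one or two exclusions.
- *That any protocol deviation triggers exclusion.* The rule is narrower: it covers treatment given when the CIP's conditions were not all met, although those conditions are not listed.

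The defect is therefore incomplete coverage of exposed subjects, not a demonstrated directional bias.

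**What to change.** In Section 7.1, keep the rule that these subjects do not count toward the sample size, limit the analysis exclusion to technical success, and add:

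> The safety endpoint is summarised in all subjects in whom the index procedure was started and the ECGenius System was used or its connection attempted, regardless of CIP deviation, subject to valid consent for use of the data.

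Align the SAP with this wording; if it already defines such a set, only 7.1 needs to change. No change to the technical-success analysis set is needed for this point.

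Cost: a short protocol amendment, which needs EC approval before implementation (8.8), and matching SAP text. No new data are required, because these subjects already complete follow-up and their events and deficiencies are already on CRFs. The one downside for the sponsor is that the safety summary may look slightly less favourable.

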7.2 DESCRIPTIVE ANALYSES

Continuous variables will be summarized using standard quantitative statistics: number of available observations, mean, standard deviation, median, quartiles, and range (minimum and maximum observed values). The number of missing observations, if any, will also be summarized.

Categorical variables will be summarized using classical frequency statistics: number of non-missing observations and percentages by categories. Number and percent of missing data, if any, will also be summarized.

There are no predefined criteria for terminating the study based on statistical outcomes. Missing data will not be replaced or imputed.

Additional statistical considerations are detailed in the Statistical Analysis Plan (SAP).

8. STUDY CONDUCT

8.1 STUDY COMPLIANCE

This Study will be conducted in compliance with the CIP, the signed Clinical Study Agreement and with the ethical principles stated in the latest version of the Declaration of Helsinki (2013), the applicable guidelines for good clinical practices, EU MDR 2017/745, EN ISO 14155:2020 (Clinical Investigation of Medical Devices for Human Subjects – Good Clinical Practice), and the applicable local and international regulations, in order to provide the greatest protection of the individual. Any deviations from the CIP that may affect the safety and welfare of study participants will be immediately reported to the Sponsor and to the Ethics Committee (EC) per each institution's guidelines.

8.2 ETHICS COMMITTEE (EC) AND COMPETENT AUTHORITY (CA)

The Study will not start without the written approval of the EC and the Competent Authority. Upon Study termination, if applicable, the Competent Authorities and ECs will be notified.

By signing the Clinical Study Agreement, the investigator is assuring that an EC will be responsible for the initial and continuing review of the proposed Study. A copy of the EC approval letter for the CIP, the informed consent, and the CIP signature page must be submitted to the Sponsor or its Designee prior to release of investigational supplies to the study site. The approval letter must refer to the specific CIP and the informed consent form. Any Investigator who is also a member of the EC is not to participate in the study approval decision. This non-participation must be noted in the approval letter. The study site must maintain an accurate and complete record of all reports, documents and other submissions made to the EC concerning this CIP.

Any report of withdrawal of EC approval will be submitted to the Sponsor or its Designee within five (5) working days.

The Sponsor or its Designee is responsible for obtaining regulatory approval for the Study from the Competent Authority. No subjects may be enrolled in the Study until written notification of such approval has been given by the Sponsor. The Sponsor or its Designee is responsible for reporting SAE and Device Deficiencies that might have led to a SADE as appropriate to the relevant Competent Authority. The Sponsor or its Designee is responsible to provide the relevant Competent Authority with the study final report within 12 months of the study termination.

8.3 INFORMED CONSENT PROCESS

It is the responsibility of the Investigator to inform each subject prior to the screening evaluation, of the purpose of this Study, including possible risks and benefits and document the informed consent process in the subject's chart. Any changes made to the informed consent must be approved by the Sponsor or its Designee, prior to submission to an EC. After approval by the Sponsor or its

Designee, the informed consent must be submitted to and approved by the applicable EC.

The process of obtaining informed consent at a minimum shall include the following steps:

- Ensure that the principal investigator or its authorized Designee conducts the informed consent process
- Include all aspects of the clinical investigation that are relevant to the subject's decision to participate throughout the clinical investigation
- Avoid any coercion or undue improper influence on, or inducement of, the subject to participate
- Not waive or appear to waive the subject's legal rights
- Use native non-technical language that is understandable to the subject
- Provide ample time for the subject to read and understand the informed consent form and to consider participation in the clinical investigation
- Include personally dated signatures of the subject and the principal investigator or an authorized Designee responsible for conducting the informed consent process
- Provide the subject with a copy of the signed and dated informed consent form and any other written information
- Ensure important new information is provided to new and existing subjects throughout the clinical investigation

One original informed consent form is to be retained by the study site and a copy is to be given to the subject. The informed consent process must be documented in the subject's source/medical record.

The informed consent must be written in a language in which the subject is fluent. If a foreign language translation is required, a statement of certification of the translation must be issued. Regulations require that foreign language informed consent forms be submitted to the EC for approval. The investigator must forward a copy of the consent form, the certified foreign language translation and an EC approval letter to the Sponsor or its Designee.

8.4 PROTOCOL DEVIATIONS

The Investigator is not allowed to deviate from the protocol.

Under emergency circumstances, deviations from the Clinical Study Protocol to protect the rights, safety, and well-being of human subjects may proceed without prior approval of the Sponsor and the EC. These deviations will be reported to the Sponsor and the EC as soon as possible after detection, but no later than 24-hours from the time of the deviation, as required.

Deviations must be documented on the appropriate Protocol Deviation CRF. If a Clinical Monitor becomes aware that an Investigator is not complying with the signed Investigator's Agreement, the Clinical Study Protocol, the requirements of GCP/ICH Guidelines or other applicable regulations, or any conditions of approval imposed by the reviewing EC, the Sponsor or designee will immediately either secure compliance or terminate the Investigator's participation in the investigation. The Investigator will be required to return all investigational components of the study device and system unless this action would jeopardize the rights, safety, or welfare of a patient.

Protocol deviations will be analyzed by the Sponsor for the impact to the overall integrity of the study. Disqualification is warranted when an Investigator has repeatedly or deliberately violated governing regulations or has repeatedly or deliberately submitted false information in any report. Where protocol deviations occur, which do not warrant disqualification from a study, the Sponsor or designee will implement appropriate corrective and preventive actions, including repeat training as deemed necessary.

8.5 STUDY TRAINING

The study device is intended for use by experienced medical personnel. The Investigator and study staff will receive Sponsor-led training on the proper use of the device to ensure the study team is familiar with its use prior to study enrollment and participation.

The study center will undergo a study initiation visit including but not limited to a review of the following:

- Study Protocol
- Study Procedures and Assessments
- Process for obtaining Informed Consent and completing Informed Consent Form
- Reporting requirements
- electronic Case Report Form (eCRF) completion and Good Documentation Practices
- Study device overview, usage, and accountability
- Protection of patient confidentiality
- Good Clinical Practices

